6.8.3. Immune Cell Phenotyping

To address the effects of GSK2831781 on the LAG-3 expressing cells in the T cell compartment, regulatory, memory and effector T cells may be assessed.

Markers may include but are not restricted to: CD3, CD4, CD8, CD14, CD16, CD19, CD25, CD45, CD56, CD45RA, CD95, CD127, CD197 (CCR7), CCR6, CXCR3 and LAG-3 as data permit.

CD107a, CD69, CD11b expression may be explored on NK cells to investigate the effect of GSK2831781 on NK cell function.

To monitor effects on specific blood leukocytes absolute counts for T, B and NK cells may be measured by flow cytometry or other technologies (e.g. chip cytometry).

6.8.4. LAG-3 Cell Receptor Occupancy

The binding of GSK2831781 to cell surface LAG-3 may be measured (bound and free) using competitive and non-competitive anti-LAG3 antibodies.

6.8.5. NK CD16 Cell Receptor Occupancy

The binding of GSK2831781 to CD16 may be measured (bound and free).

6.8.6. Serum Protein Analysis

6.8.6.1. Assessment of serum cytokines

Pro- and anti-inflammatory cytokine production will be assessed at the end of the study or may be assessed at the end of each cohort.

Granulocyte-Colony Stimulating Factor [G-CSF] samples may be taken and analysed as an exploratory biomarker.

6.8.6.2. Assessment of sLAG-3 receptor occupancy

Levels of sLAG-3 bound and unbound to GSK2831781 may be measured using ECL assays.

6.8.7. Novel Biomarkers

With the subject's consent, skin tissue and blood sample(s) will be collected during this study and may be used for the purposes of measuring novel biomarkers to identify factors that may influence psoriasis or the DTH challenge immune response, and/or medically related conditions, as well as the biological and clinical responses to GSK2831781. If relevant, this approach will be extended to include the identification of biomarkers associated with adverse events.

Samples will be collected at the timepoints indicated in Section 6.1. The timing of the collections may be adjusted on the basis of emerging PK or PD data from this study or other new information in order to ensure optimal evaluation of the PD endpoints.

Novel candidate biomarkers and subsequently discovered biomarkers of the biological response associated with psoriasis or the DTH challenge immune response or medically related conditions and/or the action of study treatment may be identified by application of

- RNA transcriptome analysis of blood and skin tissue samples.
- Measurement of the levels of a subset of RNA species on blood and skin tissue samples.

All samples will be retained for a maximum of 15 years after the last subject completes the trial.

6.8.7.1. RNA Transcriptome Research

An exploratory whole human genome expression array analysis may be conducted on blood and the punch skin biopsies from the DTH biopsies and from psoriasis patients using RNA sequencing, microarray, and/or alternative equivalent technologies, which facilitates the simultaneous measurement (and confirmation) of the relative abundances of thousands of RNA species resulting in a transcriptome profile for each skin sample. That will enable the evaluation of changes in transcriptome profiles that may correlate with biological response relating to the DTH immune challenge or psoriasis (Part A and Part B respectively) or the action of GSK2831781.

The same samples may also be used to confirm findings by application of alternative technologies.

6.8.7.2. RNA Expression Research of a Subset of RNA Species

RNA expression studies may be conducted using quantitative RT-PCR, and/or alternative equivalent technologies, which can facilitate the simultaneous measurement of the relative abundances of hundreds of RNA species resulting in a RNA expression profile for each blood and skin tissue sample. The RNAs assayed may include LAG-3 itself and other mRNAs that maybe involved with the pathogenesis of psoriasis or the DTH challenge immune response, the absorption, distribution, metabolism, or excretion of GSK2831781, or in the subject's response to GSK2831781. In addition continuing research may identify other proteins or regulatory RNAs that may be involved in response to GSK2831781 or the pathogenesis of psoriasis or the DTH challenge immune response. The RNAs that code for these proteins and/or regulatory RNAs may also be studied. This will enable the evaluation of changes in RNA expression profiles that may correlate with biological response relating to psoriasis or the DTH challenge immune response and medically related conditions or the action of GSK2831781.

In part B the samples expression of specific genes may include, but not limited to, Ki67, K16, IL-1 β , IL-6, IL-8, IL-10, IL-12, IL-17, IL-22, IL-23, INF- γ , TNF- α , iNOS, IL-1R antagonist, PGC-1 α , NCoR, NF $\kappa\beta$, FOXO, p300, PPAR α , PPAR-delta, and p53.

6.9. Pharmacogenetics

Information regarding pharmacogenetic (PGx) research is included in Appendix 2 Pharmacogenetic research. The IRB/IEC and, where required, the applicable regulatory agency must approve the PGx assessments before these can be conducted at the site. In some cases, approval of the PGx assessments can occur after approval is obtained for the rest of the study. If so, then the written approval will clearly indicate approval of the PGx assessments is being deferred and in most cases, the study, except for PGx

assessments, can be initiated. When PGx assessments will not be approved, then the approval for the rest of the study will clearly indicate this and therefore, PGx assessments will not be conducted.

7. ADVERSE EVENTS AND SERIOUS ADVERSE EVENTS

7.1. Adverse Events (AE) and Serious Adverse Events (SAEs)

The investigator or site staff is responsible for detecting, documenting and reporting events that meet the definition of an AE or SAE.

7.1.1. Time period for collecting AE and SAE information

AEs will be collected from the start of Study Treatment and until the follow-up contact.

Between follow-up and the surveillance visits only listed targeted medical events (see Section 3.4) will be reported and databased as SAEs/AEs.

Subjects will be issued with a diary to record adverse events and concomitant medications during the study. This document will be used to assist subject recall in discussions with the investigator, for site staff to then enter as appropriate into the eCRF.

Medical occurrences that begin prior to the start of study treatment but after obtaining informed consent may be recorded on the Medical History/Current Medical Conditions CRF.

SAEs will be collected over the same time period as stated above for AEs. However, any SAEs assessed as related to study participation (e.g., protocol-mandated procedures, invasive tests, or change in existing therapy) or related to a GSK product will be recorded from the time a subject consents to participate in the study up to and including any follow-up contact. All SAEs will be recorded and reported to GSK within 24 hours, as indicated in Appendix 4.

Investigators are not obligated to actively seek AEs or SAEs in former study participants. However, if the investigator learns of any SAE, including a death, at any time after a subject has been discharged from the study, and he/she considers the event reasonably related to the study treatment or study participation, the investigator would promptly notify GSK.

NOTE: The method of recording, evaluating and follow-up of AEs and SAEs plus procedures for completing and transmitting SAE reports to GSK are provided in Appendix 4.

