† All subjects in Cohort 7 have already completed the day 230 ± 7 follow up visit. Any subjects in Cohort 7 who have not had a 12-month surveillance visit when the amendment is approved should instead have a surveillance telephone call as their last study visit (see Table 6), as soon as practically possible after the amendment is approved, rather than waiting to month 12 after dosing. Subjects in Cohort 8 who have already completed their follow up visit should also have a surveillance telephone call as soon as the protocol amendment is approved. Subjects in Cohort 8 and Cohort 9 who have not yet had a follow up visit when the protocol amendment is approved should have a combined follow up/surveillance visit at day 183 ± 7, or as soon as practically possible if they have already been monitored for longer than 183 ± 7 days after dosing.

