For cohorts 3, 4 and 6, one active and one placebo subject will be recruited initially. After the GSK medical monitor and investigator have reviewed the safety data up to 48 hours post dose, an additional 5 active and 1 placebo subjects will be dosed (no more than 2 subjects per day with dosing separated by at least 1 hour).

After the DEC have reviewed the safety data up to 28 days on all subjects within the cohort along with the available PK data, a dose escalation may occur to the next planned dose. If safety findings are noted in the active subjects in cohorts with 2 subjects, the cohort may be expanded to a maximum cohort size of 6:3 (active:placebo) or the escalation stopped (See Section 5.5). Once data up to 28 days post dose has been collected for all subjects within cohort 6, the DEC will review the safety data along with the available PK data, available PD data from cohort 6 and also the DTH clinical response data from the Healthy Volunteer (DTH) cohort 5 (below), before switching to patients with plaque psoriasis.

A study schematic giving an overview of the visits is in Section 3.1.

Screening – Subjects will attend screening up to 35 days before dosing.

Day -1 – Day 4 – Subjects will attend the unit on Day -1 and will remain resident in the unit until Day 4. Provided that there are no safety issues on Day 4 (72 hours post dose) and there are no clinically significant haematology results from the 72 hour post-dose safety sample the subject will be discharged from the unit.

Days 8 and beyond - Subjects will attend the unit as an out-patient.

Follow-up - Subjects will return for a follow-up as specified in Table 1.

All subjects in cohorts 1, 2, 3 and 4 will attend a surveillance visit at 6 and 12 months. As the follow-up visit is at approximately 6 months (190 days post-dose, as per Table 1), subjects in the 0.15mg/kg cohort 6 do not require an additional post-dose surveillance visit at 6 months and will only attend a surveillance visit at 12 months.

Healthy volunteers with DTH

One active and one placebo subject will be recruited initially. After the GSK medical monitor and investigator have reviewed the safety data up to 48 hours post dose, an

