6.3.5. Immunosuppression, Infections and Malignancies

As with other immunomodulating agents, the mechanism of action of GSK2831781 could increase the possibility of immunosuppression resulting in an increase in the frequency and/or severity of infection and/or an increased risk of malignancy. Therefore, the protocol will exclude subjects who may be at increased risk of infection or malignancy based on medical/medication history and screening physical examination or laboratory findings. During the trial, subjects will be questioned at all study visits about adverse events and results recorded in the electronic case report form (eCRF). Specific attention will be given to monitoring for infection, although the single dose design with limited follow-up means that specific monitoring for malignancies is not supported.

Examinations and laboratory evaluations will be performed routinely and the results, including markers of potential immunosuppression, will be reported to the investigators. Blood samples may be collected from subjects with infections, including flu like

symptoms, during the study for analysis of LAG-3+ cells. Serology for CMV and EBV will be performed at baseline to identify subjects with potential risk of viral reactivation for these viruses. Blood samples for viral load monitoring (CMV, EBV, HSV, VZV) will be taken at baseline and archived. If the subject demonstrates any clinical symptoms consistent with viral reactivation e.g. fever, then another sample would be taken and this and the baseline sample sent for analysis and/or other appropriate medical investigations as suggested by the clinical context.

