7.1.4. Definition of Serious Adverse Events

If an event is not an AE per Section 7.1.3, then it cannot be an SAE even if serious conditions are met (e.g., hospitalization for signs/symptoms of the disease under study, death due to progression of disease, etc).

An SAE is any untoward medical occurrence that, at any dose:

- a. Results in death
- b. Is life-threatening

NOTE: The term 'life-threatening' in the definition of 'serious' refers to an event in which the subject was at risk of death at the time of the event. It does not refer to an event, which hypothetically might have caused death, if it were more severe.

c. Requires hospitalization or prolongation of existing hospitalization

NOTE: In general, hospitalization signifies that the subject has been detained (usually involving at least an overnight stay) at the hospital or emergency ward for observation and/or treatment that would not have been appropriate in the physician's office or out-patient setting. Complications that occur during hospitalization are AEs. If a complication prolongs hospitalization or fulfills any other serious criteria, the event is serious. When in doubt as to whether "hospitalization" occurred or was necessary, the AE should be considered serious.

Hospitalization for elective treatment of a pre-existing condition that did not worsen from baseline is not considered an AE.

d. Results in disability/incapacity, or

NOTE: The term disability means a substantial disruption of a person's ability to conduct normal life functions. This definition is not intended to include experiences of relatively minor medical significance such as uncomplicated headache, nausea, vomiting, diarrhea, influenza, and accidental trauma (e.g. sprained ankle) which may interfere or prevent everyday life functions but do not constitute a substantial disruption.

- e. Is a congenital anomaly/birth defect
- f. Medical or scientific judgment should be exercised in deciding whether reporting is appropriate in other situations, such as important medical events that may not be immediately life-threatening or result in death or hospitalization but may jeopardize the subject or may require medical or surgical intervention to prevent one of the other outcomes listed in the above definition. These should also be considered serious. Examples of such events are invasive or malignant cancers, intensive treatment in an emergency room or at home for allergic bronchospasm, blood

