7.1.6. Death Events

In addition, all deaths, whether or not they are considered SAEs, will require a specific death data collection tool to be completed. The death data collection tool includes questions regarding cardiovascular (including sudden cardiac death) and non-cardiovascular death.

This information should be recorded within one week of when the death is first reported.

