7.1.7. Prompt Reporting of SAEs to GSK

Once the investigator determines that an event meets the protocol definition of an SAE, the SAE will be reported to GSK within 24 hours. Any follow-up information on a previously reported SAE will also be reported to GSK within 24 hours.

If the investigator does not have all information regarding an SAE, he/she will not wait to receive additional information before notifying GSK of the event and completing the appropriate data collection tool. The investigator will always provide an assessment of causality at the time of the initial report as described in Appendix 4.

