New or updated information will be recorded in the originally completed data collection tool. The investigator will submit any updated SAE data to GSK within the designated reporting time frames.

Reporting of SAEs to GSK

The primary mechanism for reporting SAEs to GSK will be the electronic data collection tool. If the electronic system is unavailable for greater than 24 hours, the site will use the paper SAE data collection tool and fax it to the GSK Medical Monitor or protocol

contact. Then the site will enter the serious adverse event data into the electronic system as soon as it becomes available.

After the study is completed at a given site, the electronic data collection tool (e.g., InForm system) will be taken off-line to prevent the entry of new data or changes to existing data. If a site receives a report of a new SAE from a study participant or receives updated data on a previously reported SAE after the electronic data collection tool has been taken off-line, the site can report this information on a paper SAE form or to their GSK protocol contact by telephone.

GSK contacts for SAE receipt can be found at the beginning of this protocol on the Sponsor/Medical Monitor Contact Information page.

Facsimile transmission of the SAE data collection tool is the preferred method to transmit this information to the project contact for SAE receipt. In rare circumstances and in the absence of facsimile equipment, notification by telephone is acceptable, with a copy of the SAE data collection tool sent by overnight mail. Initial notification via the telephone does not replace the need for the investigator to complete and sign the SAE data collection tool within the designated reporting time frames.

12.5. Appendix 5: Modified List of Highly Effective Methods for Avoiding Pregnancy in FRP and Collection of Pregnancy Information

12.5.1. Modified List of Highly Effective Methods for Avoiding Pregnancy in Females of Reproductive Potential (FRP)

The list does not apply to FRP with same sex partners or for subjects who are and will continue to be abstinent from penile-vaginal intercourse on a long term and persistent basis, when this is their preferred and usual lifestyle. Periodic abstinence (e.g. calendar, ovulation, symptothermal, post-ovulation methods) and withdrawal are not acceptable methods of contraception.

- 1. Contraceptive subdermal implant
- 2. Intrauterine device or intrauterine system

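### Protocol 7.1.1 limits late SAEs, as well as AEs, to a loosely defined list, so a non-fatal, unlisted SAE judged unrelated need not be recorded between follow-up and the surveillance contact

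*Protocol*

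**What the plan says.** Protocol 7.1.1 collects AEs from the start of treatment to the follow-up contact, and SAEs over the same period. For the interval after that it says: "Between follow-up and the surveillance visits only listed targeted medical events (see Section 3.4) will be reported and databased as SAEs/AEs". Section 3.4 is Risk Management. It contains Table 5, which sets out potential risks of the product, the challenge agent and the procedures, with a mitigation for each. Nothing there is labelled as a list of targeted medical events.

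Table 6 footnote e restricts the surveillance telephone call to relevant AEs and SAEs and refers to Section 7 for what is relevant. Section 7 refers back to Section 3.4.

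Several provisions pull the other way:

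- 7.1.1 also says that every SAE is to be recorded and reported within 24 hours.
- 7.1.7 says: "Once the investigator determines that an event meets the protocol definition of an SAE, the SAE will be reported to GSK within 24 hours".
- 7.1.6 says that "all deaths, whether or not they are considered SAEs, will require a specific death data collection tool".
- Appendix 4 leaves a route open after the electronic form is closed, beginning "If a site receives a report of a new SAE from a study participant".

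On the SAP side, 14.2.2 puts events that occur between the last scheduled visit and the surveillance visit into the AE listing with an off-treatment flag.

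**The concern.** Safety and tolerability is the primary objective of this first-in-human study. Protocol 3.3.1 explains the late Part A visits by the possibility that pharmacodynamic effects outlast the drug. A contact made for that reason should not leave it unclear whether a serious illness reported there goes into the database.

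Suppose a subject mentions at a surveillance call a hospital admission after a road accident, and the investigator judges it unrelated. A site following 7.1.1 can leave it out. A site following 7.1.7 would report it. Causality judgements can change on follow-up, as Appendix 4 allows, but an event that was never recorded cannot be looked at again.

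The SAP plans listings of all AEs and of serious AEs. Without a caveat, a reader of those listings would take the late SAE data as complete.

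**Working it through.** **Text check: does any provision bring back a non-fatal, unlisted, unrelated SAE in this interval?**

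| Provision | What it covers | Covers this case? |
|---|---|---|
| 7.1.1, restricted interval | Section 3.4 events only, SAEs named | No |
| 7.1.1, SAEs from consent to any follow-up contact | SAEs related to participation or to a sponsor product | No, needs relatedness |
| 7.1.1, SAEs learned of after discharge | SAEs considered reasonably related | No, needs relatedness |
| 7.1.1, all SAEs recorded and reported in 24 hours | No stated limit, but can be read as handling SAEs inside the collection period | Unclear |
| 7.1.6 | Deaths | No, the case is non-fatal |
| 7.1.7 | Any event meeting the SAE definition, 24-hour clock | Unclear, for the same reason |
| Appendix 4 | A site can report a new SAE after the electronic form closes | A permitted route, not a collection rule |

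No provision clearly restores it, and two could be read either way.

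**Person-time the fix can still reach (Part B calls).** The Table 1 footnote says that Cohort 7 subjects without a 12-month visit "should instead have a surveillance telephone call as their last study visit". Cohort 8 subjects who have already had follow-up also get a call. Subjects with the combined follow-up and surveillance visit have no gap. Inputs are 9 subjects per cohort, nominal follow-up at 230 days (Cohort 7) and 270 days (Cohort 8, before Amendment 10), and 12 months taken as 365 days.

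- Cohort 7: 9 × (365 − 230) = 9 × 135 = 1,215 days
- Cohort 8: 9 × (365 − 270) = 9 × 95 = 855 days
- Total: 1,215 + 855 = 2,070 person-days; 2,070 / 365 = 5.67 person-years

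This is a ceiling at nominal days. It assumes that every subject in both cohorts gets a call (the Cohort 8 number is not given) and that calls come as late as month 12, whereas the footnote asks for them as soon as practical. A follow-up visit 7 days early would add at most 18 × 7 = 126 days.

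The documents give no rate for such SAEs. Assuming 0.5% to 5% per person-year, the expected number is 5.67 × 0.005 = 0.03 to 5.67 × 0.05 = 0.28.

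**Part A, for context only.** Restricted days per subject are 365 minus the Table 1 follow-up day (28, 42, 84, 146, 190, 190 post-dose), with 2, 2, 8, 8, 12 and 8 subjects:

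337×2 + 323×2 + 281×8 + 219×8 + 175×12 + 175×8 = 674 + 646 + 2,248 + 1,752 + 2,100 + 1,400 = 8,820 person-days.

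Most of this had passed by Amendment 10. By then all of Cohort 7 had completed follow-up, so each was at least 230 − 7 = 223 days post-dose. Each cohort waits for 28-day data from the one before (for the switch to patients: "Once data up to 28 days post dose has been collected for all subjects within cohort 6"), and Cohorts 3 to 7 add a 48-hour sentinel wait.

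- Minimum days post-dose, Cohorts 6 to 1: 253, 283, 313, 343, 373, 401
- Most that can remain: 112×8 + 82×12 + 52×8 + 22×8 = 896 + 984 + 416 + 176 = 2,472 days
- At least 8,820 − 2,472 = 6,348 days had elapsed (72%)

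**The case against.** The strongest reply is that this is a deliberate choice of collection window. Full collection runs to a follow-up visit timed to when drug levels were predicted to be around the in vitro EC50, and actual clearance was much faster than predicted. Related SAEs, deaths and the listed risks are kept throughout. That stands as a reason for targeting non-serious AEs late in the study. It is weaker as a reason to leave out a serious event the subject has already reported.

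Three stronger readings are tempting and are not supported:

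- **That 7.1.1 and 7.1.7 flatly contradict each other.** 7.1.7 is headed as a prompt-reporting rule. It can be read as setting the clock for SAEs that fall inside the 7.1.1 window, and the sentence in 7.1.1 about recording all SAEs can be read the same way. What remains is an ambiguity.
- **That malignancies would be lost because Table 5 omits them.** Protocol 6.3.5 says the mechanism could lead to an increase in "infection and/or an increased risk of malignancy", and 7.1.4 says of SAEs: "Examples of such events are invasive or malignant cancers". But several row labels of Table 5 are missing from the text available here, so absence cannot be shown, and a malignancy judged related would be kept in any case. No claim is made about malignancy.
- **That the Part A person-time measures lost safety data.** It measures calendar time under the rule, nearly three quarters of it or more already past, and the current Table 6 has no Part A surveillance column.

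It is also fair that a wording change needs a protocol amendment, and that the Part B calls were due soon after Amendment 10, so the change could come too late for some or all of them.

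**Conclusion.** The point holds as a cheap improvement of low severity. On its literal wording, 7.1.1 allows a non-fatal SAE outside the Section 3.4 table and judged unrelated to go unrecorded between follow-up and the surveillance contact. The provisions that might override this are ambiguous.

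The size is individual late cases at most. The 2,070 person-day bound for the remaining Part B calls rests on nominal follow-up days, full cohorts and calls as late as month 12. The expected count of well under one event rests on an assumed rate. A reader might infer that the trial's safety conclusions are compromised. The documents do not support that, because dose escalation, stopping rules and treatment-emergent summaries do not depend on this interval.

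**What to change.** In Protocol 7.1.1, state that all SAEs, regardless of causality or listing, are recorded from first dose to the last study contact, and keep the targeted-event restriction for non-serious AEs only. Table 6 footnote e then follows without editing, because it defers to Section 7, and the ambiguity with 7.1.7 goes away. No SAP change is needed.

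For surveillance contacts completed under the current protocol wording, add one line to the study report saying that unlisted, unrelated SAEs in that interval may not have been collected. If the amendment comes after the last call, this line is the whole remedy.

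The cost is a protocol wording amendment, a few extra SAE forms and one sentence in the report. No subject needs to be contacted again.
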